14.1.3 Part C (phase IIa) Pharmacokinetic Cohort

At least 10 patients (up to a maximum of 20 patients, all treated with the “40/15” treatment regimen) will be entered into Part C. This number is based on feasibility and the minimum number of patients evaluable for pharmacokinetic analyses (profiles and pharmacokinetic parameter summaries).

For the purpose of pharmacokinetic parameter evaluation and analysis, patients with FL entered into Part B who have also provided PK samples, and who are treated with “40/15” treatment regimen may be combined with patients entered into Part C.

14.1.4 Analysis Populations

Definition of populations

The following 4 populations are defined:

- Safety: All patients who received Betalutin or lilotomab or rituximab.
- Intent-to-treat (ITT): All patients who received Betalutin.
- Per Protocol (PP): The Per Protocol population will consist of a subset of patients from the ITT population who have an adequate tumour assessment at baseline, a follow-up tumour assessment ≥ 12 weeks after starting treatment (unless disease progression is observed before that time), and no major protocol violations.
- Pharmacokinetic (PK): The PK Population will be defined as all subjects who received at least a dose of Betalutin and have evaluable PK data, and a complete or agreed sparse scheduled post-dose PK measurements without protocol deviations, violations, or events thought to significantly affect the PK of the drug.

Part A (phase I and phase IIa)

The primary efficacy analysis population is PP because in early phase study we are interested in demonstrating in principle whether the treatment is efficacious. Efficacy endpoints will also be evaluated in the ITT population.

Part B (FL Phase IIb)

The primary efficacy analyses will be conducted on the ITT population.

Part C (Pharmacokinetic Cohort, phase IIa)

The primary pharmacokinetic analyses will be conducted on the PK population.

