The study is a randomised, 2-arm, open-label study to further differentiate the risk/benefit of 2 candidate dose regimens of lilotomab and Betalutin in patients with relapsed non-Hodgkin B-cell FL.

Once approximately 50 patients have been treated (approximately 25 per dose regimen), an interim analysis was performed to evaluate the possibility of study modifications or continuation of both regimens.

The intent-to-treat (ITT) population will consist of all patients who were randomised to one of the dose groups. The primary efficacy endpoint is ORR. Scans will be performed at baseline, 3, 6, 9, 12, 18 and 24, 36, 48 and 60 months after Betalutin injection for all patients to assess tumour response as follows:

- CR
- PR
- No change/stable disease (SD)
- PD
- NE

Response rates will be presented as percentage of patients in the ITT population with the exact 95% confidence interval (Clopper-Pearson).

Assessment of ORR in the “40/15” treatment regimen.

A total of 87 patients, including the ones in the interim analysis, will be recruited and treated with the “40/15” regimen.

The response rate under the null hypothesis is set at 30%, versus the response rate of 48% under the alternative hypothesis will be compared. A 2-sided exact test with a significance level of 0.05 will be used to compare the observed response rate against the hypothesis. In addition, a complete response rate of 8% under the null hypothesis versus a complete response rate of 20% under the alternative hypothesis will also be tested.

Descriptive and summary statistics will be calculated for each pharmacokinetic parameter. Further analyses may be conducted, as appropriate. Pharmacokinetic data and/or parameters from patients who received lilotomab 40 mg and Betalutin 15MBq/kg in Part B may be combined with data from Part C.

Safety Review Committee:

Part A:

The recommendation to increase or decrease the dose in Part A has been made by the SRC based on the safety data in the database at the time until the last patient in the current cohort has onset of blood counts recovery. The SRC consists of 3 to 4 relevant experts including the coordinating investigator for the study.

Part B:

The SRC will periodically monitor the safety data.

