Open label phase IIa expansion cohort to enable the collection of samples for Betalutin pharmacokinetics and total lilotomab antibodies pharmacokinetics in at least 10 patients (up to a maximum of 20 patients) receiving the “40/15” regimen.

Figure 6-1 ` LYMRIT 37-01 Study Design (Part A, Part B and Part C)

- Part A is closed to enrolment.
- Part B (PARADIGME) is open to enrolment for patients with FL.
- Part C (Pharmacokinetic Cohort) is open at selected sites (subject to regulatory and EC/IRB Approvals) to enrolment for patients with iNHL. All patients will receive the “40/15” regimen. Patients entering Part C will follow the same Schedule of Assessments (except QoL) as those in Part B.

Definition of study periods:

The *study treatment period* is defined as from the first administration of rituximab pre-treatment until 12 weeks after Betalutin administration. All patients will be closely monitored during the study treatment period.

The *follow-up period* is

Part A - up to 5 years or until the first anticancer treatment after Betalutin administration. Survival and potential long-term toxicity information will continue to be collected up to 5 years, even after further anticancer treatment has begun. All patients will be followed closely the first year after treatment, thereafter every 6 months (See [Section 6-3](#) Schedule of Assessments).

Part B and Part C - up to 5 years after Betalutin administration.

Extensive follow-up (hospital visits) will take place for all patients every 3 months for the first year (Months 6, 9 and 12). Tumour imaging assessments are only required until the patient has further anticancer treatment after Betalutin administration or disease progression prior to further anticancer therapy as assessed by central imaging review. All other scheduled assessments should be performed.

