3.2.2 Efficacy Analysis set

Efficacy Analysis set will be a subset of the Part B participants who received Betalutin and were assigned either “40/15” or “100/20” dose levels.

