3.4 Data Presentation

The TFLs will present the dose regimens (where relevant) as detailed below:

Table 4: LYMRIT-37-01 study, Part B/C Treatment Group Descriptors

Order	Descriptor for Dose Regime (where relevant) to be presented in TFLs	Meaning of Descriptor
1 [1]	40 / 12.5	40 mg lilotomab plus 12.5 MBq/kg Betalutin
2	40 / 15	40 mg lilotomab plus 15 MBq/kg Betalutin
3	100 / 20	100 mg/m ² lilotomab plus 20 MBq/kg Betalutin
4 [1]	Received Rituximab only	Received Rituximab only
5 [1]	Enrolled no treatment	Enrolled but did not receive any trial treatment
6 [1]	Screen failure	Participants in the screened set who failed screening (i.e. are not eligible to join the study per the eligibility eCRF page).

[1] In table summaries, if there is insufficient space to present all treatment groups on a single page, these dose regimens will be presented on the next page.

The data will be summarised in tabular form by Study Part (i.e. B / C) and dose regimen.

Results from scheduled visits will be tabulated. Unscheduled visits will be included in assessments of maximum post-baseline. All assessments will be listed.

Table 5: Populations to be used for output

Type of data	Listings	Summaries
Disposition	Screened set	Screened set
Demographic characteristics and baseline	SAF	SAF, Efficacy Analysis Set
Efficacy	SAF	Efficacy Analysis set

AE's and lab data	SAF	SAF
-------------------	-----	-----

Listings will be sorted by Study Part (i.e. B / C) and dose regimen, patient number and date/time of assessment.

Graphical presentations of the data will also be provided where appropriate.

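### The protocol defines ITT in two conflicting ways for Part B, and the SAP adopts the Betalutin-received version without explanation, so assigned but undosed patients leave the response denominators

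*Protocol*

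**What the plan says.** **Protocol.** Section 14.1.4 states: "Intent-to-treat (ITT): All patients who received Betalutin". In the synopsis, under the comparison of the two Part B regimens, the text is: "The intent-to-treat (ITT) population will consist of all patients who were randomised to one of the dose groups". Both are current text, not amendment history. For Part B, section 14.1.4 then says: "The primary efficacy analyses will be conducted on the ITT population". It does not say which definition governs. Section 14.1.7 plans a Fisher's exact comparison of ORR in the randomised period and, for 40/15, a test of ORR against 30%.

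**Timing.** Rituximab is given on Day -14 and Betalutin on Day 0. Protocol 6.1 says that the study treatment period "is defined as from the first administration of rituximab pre-treatment until 12 weeks after Betalutin administration". An assigned patient can therefore start study treatment and not reach Betalutin.

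**SAP.** No set is called ITT. Section 3.2.2 reads: "Efficacy Analysis set will be a subset of the Part B participants who received Betalutin", with the further condition of assignment to 40/15 or 100/20. Section 3.7 bases all efficacy analyses on that set. Table 4 in section 3.4 provides display groups for "Received Rituximab only" and for patients described as "Enrolled but did not receive any trial treatment". Neither group is split by assigned regimen. Section 3.10 attributes the changes from the protocol to early termination in general terms and does not mention the choice of population.

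**The concern.** The same label covers two different denominators for the primary endpoint. Under the synopsis, a randomised patient who progresses, withdraws or fails the Day -1/0 checks after rituximab stays in. Under section 14.1.4 that patient is out.

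The SAP plainly foresees such patients. Besides the Table 4 groups, section 3.6.3.3 reserves regimen number 99 for earlier Part B rituximab exposure in patients who re-enrolled, and the SAP gives no rule for counting the first enrolment. These patients are in the safety set, and their adverse events are treatment-emergent from rituximab onwards, yet they do not appear in efficacy.

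Two things are at stake. For a single regimen, removing patients who fail during the lead-in can flatter the response rate. For the randomised section, exclusion after an open-label allocation gives up the protection of randomisation, because leaving before Day 0 can depend on the known regimen. A reader of the final report who sees ITT in the protocol would also not know which denominator was promised.

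**Working it through.** **Inputs.** From protocol 14.1.2.3: 87 patients on 40/15, null ORR 30%, alternative 48%, two-sided exact test at 0.05, threshold of 36 responders, power above 90%. From SAP 3.7.1.1: a patient with no disease assessments is not evaluable, hence not a responder. The number of undosed patients, k, is not given, so it is varied from 0 to 10.

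**Step 1: the plan's own figure.** The exact (Clopper-Pearson) lower limit for x responders in n is the 2.5% quantile of Beta(x, n − x + 1).
- 36/87: lower limit 30.9%. The chance of 36 or more is 0.0157 at a true rate of 30% and 0.911 at 48%.
- 35/87: lower limit 29.85%, below 30%.

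The threshold of 36 and the power above 90% are reproduced.

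**Step 2: direction.** With x responders among N dosed patients and k undosed patients counted as not evaluable, the all-assigned rate is x/(N + k) and the dosed-only rate is x/N. Their ratio is (N + k)/N, which is never below 1. Dropping undosed patients can therefore raise the rate or leave it unchanged.

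**Step 3: size at the threshold.** Hold 36 responders and add k undosed patients to 87.

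| k | ORR | Exact 95% CI | Responders needed for lower limit above 30% |
|---|---|---|---|
| 0 | 36/87 = 41.4% | 30.9 to 52.4% | 36 |
| 2 | 36/89 = 40.4% | 30.2 to 51.4% | 36 |
| 3 | 36/90 = 40.0% | 29.8 to 50.9% | 37 |
| 5 | 36/92 = 39.1% | 29.1 to 49.9% | 37 |
| 10 | 36/97 = 37.1% | 27.5 to 47.5% | 39 |

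The lower limit crosses 30% between k = 2 and k = 3. The crossing depends on the exact method: a two-sided binomial test that sums outcomes no more likely than the one observed still gives p = 0.0497 at 36/90. The interval rule is used here because it reproduces the protocol's 36.

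The relative inflation grows as N falls. With k = 3 it is 90/87 = 1.034 at N = 87 and 64/61 = 1.049 at N = 61. The 61 is the number in the July 2022 review (SAP section 1), used only for scale.

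**Step 4: the contrast between regimens.** Take invented counts of 36/65 and 30/65, at the planned arm size. The difference is 55.4% − 46.2% = 9.2 points. Now remove undosed non-responders:
- 3 from each arm: 36/62 − 30/62 = 9.7 points
- 6 from each arm: 36/59 − 30/59 = 10.2 points
- 6 from the first arm only: 36/59 − 30/65 = 14.9 points
- 6 from the second arm only: 36/65 − 30/59 = 4.5 points

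Equal loss changes little. Only unequal loss distorts the contrast materially, and it can do so in either direction.

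**The case against.** The strongest reply is that, for 40/15, a dosed denominator is the design. Protocol 6.1 ends enrolment when 87 patients have received the regimen, and 14.1.2.3 builds the hypotheses and the threshold of 36 on those patients. Adding undosed patients asks a different question and reveals no error in the threshold. This stands, and it is why the dosed analysis should remain the main one for 40/15.

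Next, the SAP tests nothing. Section 2.4 says the terminated study is not powered for its original objectives, and section 3.7.1.2 gives each regimen a rate and an exact interval, with no test of 30% and no comparison between regimens. This also stands: crossing 30% triggers no decision, and the bias in the contrast concerns the protocol's Fisher comparison, which the SAP has dropped. Randomisation stopped after the interim analysis of 47 patients, so the SAP's 40/15 group mixes randomised and later patients in any case.

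Part of the information is already planned. SAP 3.5.2 lists set membership with reasons for exclusion and summarises reasons for withdrawal. What is missing is the split by assigned regimen and a response rate on all assigned patients.

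Finally, section 14.1.4 cannot simply copy the synopsis wording. It also serves Part A and the patients enrolled after the interim analysis, who were not randomised. The fix has to allow for that.

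**Conclusion.** The conflict between the two ITT definitions is real and sits in current text. The SAP settles it silently in favour of receipt of Betalutin. Its set is also narrower than section 14.1.4, because reduced-dose Part B patients are left out.

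A reader might infer that the reported ORR is inflated and that the symmetry between arms is broken. The documents do not support either. They give no count of undosed patients. Table 4 covers Parts B and C together, so the number assigned to 40/15 or 100/20 could be zero. The same rule and the same rituximab lead-in apply to both regimens, and no unequal loss is reported. Both effects are risks.

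The size is conditional. If undosed patients count as non-responders and exactly 36 patients respond, two undosed patients leave the exact lower limit above 30% and three take it just below. For single-arm 40/15 the point is mainly one of labelling and transparency. For the randomised section it is a possible bias of unknown size. It should be corrected, but it does not invalidate the treated-set results.

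**What to change.** 1. For Part B, state one ITT definition: all patients assigned to 40/15 or 100/20, by assigned regimen, which in the randomised section means all randomised. Rename the Betalutin-received set Treated or modified ITT. Leave the Part A sets unchanged. Record the choice and its reason in SAP 3.10.
2. Keep ORR and CRR on the treated set as the main single-arm 40/15 analysis, in line with the 87-treated design. In SAP 3.7.1.2 and 3.7.2.2 add a sensitivity ORR and CRR on all assigned patients, with undosed patients as non-responders. State how a re-enrolled patient is counted.
3. In SAP Table 4 and the disposition summary (3.5.2), show the rituximab-only and enrolled-but-untreated groups by assigned regimen, with the reason Betalutin was not given.

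The cost is small. SAP Table 2 lists a dataset that confirms randomisation and dose, so each response table needs one extra row. As the trial is terminated, and a protocol change would need a written amendment (protocol 16.2), the correction can be made in the SAP and the study report. The downside is a possibly slightly lower ORR in the sensitivity row.

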14.1.5 Statistical Methods

Results from Part A (Phase I and Phase IIa), Part B and Part C will be summarised separately due to differences in study design, dose regimens and patient populations. However, analyses in specific populations and for specific dose regimens may be performed in the overall study population.

The results from this study will be presented mostly using descriptive statistical methods. Details of planned analyses for Parts A, B and C will be provided in separate statistical analysis plans.

All statistical programming and analyses will be performed using SAS[®] software.

Data will generally be presented by time of measurement. In general, continuous variables will be described using standard summary statistics such as number of observations, mean value, standard deviation, minimum value, maximum value, median, and first and third quartiles. Categorical variables will be summarised in frequency tables as count and percentages.

All individual data collected in the eCRF will be presented in data listings. Patients screened but not included in the study will not be presented in any tables or listings.

Prior to database lock and analysis of the final study data, a detailed Statistical Analysis Plan (SAP) will be prepared and approved, describing all the analyses to be performed. The SAP will document any changes to the analyses described in this protocol.

14.1.6 Analysis of Demographic and Pre-treatment Characteristics

Demographic data and other pre-treatment characteristics (including medical and disease history) will be summarised by dosing cohort (Part A) or dosing regimen (Part B) or Part C.

For all demographic and baseline characteristics, the analysis population will be the safety population.

Administration of the IMP will be listed provided in listings, by cohort and patient.

14.1.7 Analysis of Efficacy Data

Tumour response will be reported as follows in individual patients:

- CR
- PR
- SD
- PD
- NE

In Part A and Part C: Response rate will be presented as a point estimate of the proportion of responders along with the 95 % exact confidence interval of response rate.

In Part B randomised period: The ORR will be compared between dosing regimens using the Fisher's Exact test, and the difference in response rates and the corresponding 95% exact CI will be presented. ORR estimates and 95% exact CI for each dosing regimen will also be presented.

In Part B Single-arm 40/15 part: – The primary efficacy analysis on ORR (based on independent assessment) will be performed by testing whether the ORR is less than or equal to 30% against the alternative hypothesis that ORR is greater than 20% at overall two-sided 5% level of significance, i.e.,

$H_0: p = 0.3$ vs. $H_a: p \neq 0.3$

In addition, the secondary efficacy analysis on CRR (based on independent assessment) will be performed by testing whether the CRR is less than or equal to 8% against the alternative hypothesis that ORR is greater than 8% at overall two-sided 5% level of significance, i.e.,

H0: $p = 0.08$ vs. Ha: $p \neq 0.08$

Responders are defined as having CR and PR according to definition in [Section 12.3](#).

Time to event endpoints will be analysed using standard Kaplan-Meier techniques. The estimate of the median survival curve will be calculated along with the associated 95% confidence intervals (when applicable). The efficacy endpoints are:

Overall Response Rate (ORR)

ORR, defined as the proportion of patients who achieve a CR or PR assessed with the use of standard criteria for lymphoma (1). The ORR will be assessed at 3 months image evaluation.

Best ORR will also be evaluated, taking the best response achieved independent of time point for image evaluation.

Complete Response Rate (CRR)

CRR, defined as the proportion of patients who achieve a CR assessed with the use of standard criteria for lymphoma (1). The CRR will be calculated based on complete responses achieved at any timepoint.

Progression-free survival (PFS)

PFS is defined as the interval from Betalutin administration and date of:

- Relapse (new or enlarged lesions after CR).
- Progression (new or enlarged lesions after PR or SD).
- Death from any cause.

If none of the above events are observed, PFS will be censored at the date of the last adequate tumour assessment

Duration of response (DoR)

DoR is the time from when criteria for response (CR or PR) is first met to the time of relapse or progression. Patients who have not relapsed/progressed will be censored at the last adequate tumour assessment.

Duration of Complete Response (DoCR)

DoCR is the time from when the complete response is first observed to the time of relapse. Patients who have not relapsed will be censored at the last adequate tumour assessment.

Overall survival (OS)

OS is defined as the time from administration of Betalutin to the date of death from any cause. Patients still alive or lost to follow-up are censored at the last date they were known to be alive. Patients still alive are censored at the last known date alive.

14.1.8 Biodistribution and Pharmacokinetics

These data, which are obtained from a subset of patients in Part A and B, and from all patients in Part C, as described in [Section 10](#), will be listed by patient by time point.

Individual pharmacokinetic data will be tabulated and total radioactivity in blood (Betalutin PK) and total lilotomab antibodies in serum concentration(s) (total lilotomab antibodies

pharmacokinetics) vs. time curves presented. Pharmacokinetic results will also be summarised by cohort (Part A) or dosing regimen (Part B and Part C). Pharmacokinetic parameters will be determined using non-compartments analyses including activity-corrected area under the blood radioactivity vs. time curve, dose-corrected area under the serum concentration vs. time curve clearance, apparent volume of distribution and half-life.

14.1.9 Analysis of Pharmacokinetic Data

The study population displays will be based on the PK population, unless otherwise specified.

Betalutin pharmacokinetic parameters to be determined include: Maximum total radioactivity in blood (C_{max}), time to reach maximum blood concentration (t_{max}), area under the total radioactivity-time curve ($AUC_{0-\infty}$, AUC_{0-last}), mean residence time (MRT), terminal elimination half-life ($t_{1/2, z}$), biological half-life (T_b), effective half-life (t_e) total body clearance (CL), renal clearance (CL_R), and volume of distribution (V_d). Activity-adjusted C_{max} and AUC will also be calculated using the actual activity injected (Bq).

Total lilotomab antibodies pharmacokinetic parameters to be determined include: Maximum total drug concentration in serum (C_{max}), time to reach maximum drug concentration (t_{max}), area under the drug concentration-time curve ($AUC_{0-\infty}$, AUC_{0-last}), mean residence time (MRT), terminal elimination half-life ($t_{1/2, z}$), total body clearance (CL), renal clearance (CL_R), and volume of distribution (V_d). Dose-adjusted C_{max} and AUC will also be calculated using the actual dose of antibody injected (mg) to investigate the effect of body size on the pharmacokinetics of lilotomab.

Pharmacokinetic analysis will be carried out using actual sampling times. Data will be tabulated by patient by time point. Descriptive statistics (geometric mean, standard deviation, minimum, median, and maximum) and coefficient of variation (%) will be calculated for pharmacokinetic parameters. For each of the parameters, summary statistics will be calculated and tabulated by arm and dose group. Output will be presented separately for Part A and Part B, whilst data obtained from Part B patients (treated with the “40/15” regimen) may be combined with data obtained from Part C patients. Additional analysis such as pharmacokinetic/pharmacodynamic modelling will be considered pending the size of the PK population.

